5.3 COVARIATES

The adjusted (least squares) mean and SE (standard error) from an analysis of covariance will be used to determine non-inferiority. The ANCOVA model will include treatment group, region and gender as fixed effects, with baseline age and baseline IGF-I SDS as covariates. Baseline height may also be included as a covariate if found to be significant at $p < 0.10$. Other covariates may be considered for exploratory purposes.

6. STATISTICAL METHODOLOGY AND ANALYSES

6.1 GENERAL CONSIDERATIONS

Summaries of subject disposition, demographics, disease characteristics and response to dosing of study medication will be provided for each treatment group. All summaries of continuous data will be presented as means (SD), and/or with medians, and with min/max as appropriate. Count data will be presented as number within each treatment group and % of subjects within each group.

Summaries of all adverse events (AEs), serious adverse events (SAEs) and Suspected, Unexpected Serious Adverse Reactions (SUSARs) will be reported. The incidence of CTCAE Grade 3 or 4 adverse events will be classified according to severity and relationship to study drug.

Analyses outside of this SAP may be performed to supplement results or for research purposes at the discretion of Versartis, Inc.

6.2 CHANGES FROM PROTOCOL SPECIFIED ANALYSES

Changes to the protocol may result in changes to the planned analyses, and may change the defined analysis endpoints and methods. Any changes to analysis as a result of changes to the protocol will be documented as an amendment to this SAP. Other than transformations or modeling needed to address the structure and distribution of the resulting data, additional analyses will be for exploratory purposes only.

The changes from the protocol specified analyses are:

1. Growth Hormone Binding Protein (GHBP) and Acid Labile Subunits (ALS) will be summarized but not analyzed as secondary endpoints.
2. Inclusion of Levine's test for homogeneity of variance
3. Inclusion of Welch's t-test if there is unequal variance
4. Replaced multiple imputation for missing data with tipping point analysis

6.3 STUDY HYPOTHESES

The primary comparison of the annualized height velocity between somavaratan and daily rhGH is based on the null hypothesis that the difference is less than or equal to -2.0 cm/yr, the non-inferiority margin.

6.4 HANDLING OF MISSING VALUES AND OUTLIERS

Because of subject privacy limitations, birth dates may only be reported by month and year in certain locations. Where the specific birth day is not available, the day of month will be imputed as the 15th.

For the primary endpoint in the ITT population, missing height at 12 months will be imputed from the last available height. This imputation assumes no growth after the last available measurement observed at study exit. This is an extremely conservative approach. For example, a █ year old █ subject who discontinued at month 6 with annualized HV of 6 cm/yr (Day 1 height of █ cm and Month 6 height of █) will have the height at 12 months imputed to █ cm, resulting in an annual HV of 3 cm/yr.

For the sensitivity analysis of the effect of missing data on the primary endpoint, height velocity at Month 12, a tipping point approach will be used. The missing data will be imputed as follows:

For the control group:

1. All subjects to the control group mean (calculated without subjects missing endpoint)
2. 50% to the group mean, 50% to the HV associated with each subjects last reported height (no additional gain in height)
3. Each subject's HV imputed based on its own last reported height

For the somavaratan group:

1. All subjects to the somavaratan group mean (calculated without subjects missing endpoint)
2. 50% to the group mean, 50% to the HV associated with each subjects last reported height (no additional gain in height)
3. Each subject's HV based on its own last reported height
4. Each subject imputed to HV based on last reported height, minus 1 cm.
5. Each subject imputed to HV based on last reported height, minus 2 cm (the non-inferiority margin, to avoid imputing to a common mean).

The reduction of the imputed HV by -1 and -2 cm will be limited to a minimum 0 HV, as negative HV is not possible. This will result in a total of 15 comparisons which should cover the range of plausible results for the subjects who are not able to provide Month 12 height velocity, and accounts for combinations where the somavaratan drop outs will have worse outcomes than drop outs in the control group (e.g., control group imputation 1 versus somavaratan imputations 2 to 5).

No imputations will be considered for the PP populations.

All data collected under this protocol will be included in the assessment of safety. Any AEs missing the relationship to study treatment after repeated query attempts will be assigned as "unknown." Missing or incomplete start dates will be imputed to the date of first dose. Outliers that may have undue influence on the analysis and results will be discussed, but the

results will not be based on any exclusion. No other imputation is planned for the safety population.

Based on the validated assay performed at the central laboratory, the IGF-I values have a lower limit of quantitation (LLOQ) of 16.0 ng/mL and a lower limit of detection (LLOD) of 2.5 ng/mL. As subjects are expected to have growth hormone deficiency, IGF-I values may occasionally fall below the LLOQ. In these cases, the IGF-I value will be assigned to the value midway between the LLOQ and the LLOD, which is 9.25 ng/mL.

Adjustments to the safety laboratory data (blood chemistry, hematology) and IGFBP-3 due to values being below a quantifiable level will be made to indicate a value as one-hundredth (0.01) less than or higher than the limit value (e.g. < 5.0 will be adjusted and summarized as 4.99, > 12.5 will be adjusted and summarized as 12.51).

Adjustments to the PK data due to missing values or for values being below a quantifiable level may be performed, but those will be described in a separate PK report.

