GHD in children results from a variety of genetic, neoplastic, inflammatory, post-traumatic and iatrogenic causes.⁴ Subjects with untreated childhood onset GHD will have significant growth failure with attainment of adult heights significantly less than five feet in many instances.⁶ In addition, there is abnormal body composition with decreased bone mineralization, decreased lean body mass and increased fat mass. Treatment with exogenous rhGH initiates a period of accelerated or “catch-up” growth that when begun at an early age allows attainment of normal adult height and body composition.^{5, 6, 7, 8, 9}

Daily rhGH administration does not mimic the normal endogenous pulses of hGH in non-GHD children, but nevertheless results in significant age- and dose-dependent increases in growth with typical first year responses averaging 9.5–11 cm/yr in pre-pubertal children.^{10, 11, 12} Alternative pharmacokinetic profiles for rhGH delivery can also be beneficial. Clinical studies of continuous infusion of rhGH with a pump demonstrated comparable growth velocity and IGF-I levels to those achieved with daily rhGH injections.^{13, 14, 15} Therefore, continuous, as well as pulsatile, administration of rhGH is efficacious.

Beginning in 1985, national health authorities have approved several rhGH products for daily, long-term administration to children with GHD.^{16, 17, 18, 19, 20, 21} Compliance with daily injections for the period of years required to complete childhood and pubertal growth can be a challenge. A lack of compliance with daily rhGH administration is commonplace and can lead to loss of treatment effects.^{22, 23, 24} Long-acting rhGH offers the possibilities of many fewer injections, enhanced compliance and attainment of improved treatment outcomes.

In this protocol (14VR4), long term safety, pharmacodynamics (PD), and efficacy of somavaratan will be compared to that of daily rhGH in pre-pubertal, naïve to treatment children with GHD.

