An intention to treat (ITT) population will be used for the primary evaluation of efficacy. The primary endpoint will be the non-inferiority of somavaratan treatment height velocity compared to daily rhGH after 12 months on treatment. For subjects completing less than the 12 months of treatment, missing height at 12 months will be imputed from the last available height SDS, with a reduction of 2 cm/yr for subjects in the somavaratan group. This imputation calculates the height at 12 months from the height SDS observed at study exit. This is equivalent to a subject not having gained any more height relative to the age specific height (i.e., no treatment response) since study exit. The reduction of 2 cm/yr, the non-inferiority margin, only for the somavaratan imputed value avoids imputing to a common mean.³¹ A sensitivity analysis using multiple imputation technique, assuming missing at random, will also be conducted. Baseline characteristics of these dropped subjects will be reported. A per protocol analysis for subjects completing 12 months of treatment with <10% missed or

incorrect dosing will also be performed. No imputations will be considered for the PP populations.

For the growth and bone age endpoints, the least squares means and confidence interval of the treatment groups from an ANCOVA model will be used to determine non-inferiority. The ANCOVA model will use the endpoint (e.g., height velocity) as the dependent variable, with treatment and region as fixed effects, and include age, baseline IGF-I SDS as covariates. Other covariates will be considered as appropriate. The potential treatment differences in IGF-I and IGFBP-3 responses will be evaluated with ANCOVA, with treatment and region as fixed effects, and baseline characteristics as covariates as appropriate.

The gender, age, height and weight of subjects entering puberty at one year will be described. Onset of puberty is defined as the appearance of Tanner stage 2 breast development in girls and a testicular volume ≥ 4 mL in boys.

An exploratory analysis will be conducted to determine if IGF-I responses correlate to height velocity outcomes.

Mean values and mean change from baseline for safety laboratory data will be summarized by visit and treatment group. If applicable, appropriate statistical methods may be employed to look for trends in safety variables. No formal tests of hypotheses are planned for safety parameters and no corrections for multiple comparisons will be made.

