4. ANALYSIS SETS

4.1 PRIMARY ANALYSIS POPULATION AND MODIFIED INTENT TO TREAT (mITT)

The primary analysis population (ITT, Intent-To-Treat) will be based on all randomized subjects. In addition, a mITT population, defined as all subjects completing at least one month of dosing with completed efficacy assessments at the Month 1 visit will also be created. Subjects completing less than one month of treatment or without a post-treatment height measurement will not be included in the mITT population. Based on previous studies with somavaratan, the expectation is that very few subjects who randomize will not be able to complete at least 1 month of treatment and evaluations.

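### The SAP's primary imputation freezes height at exit in both arms and drops the somavaratan-only 2 cm/yr reduction, so control drop-outs push the result toward non-inferiority

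*SAP*

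**What the plan says.** Protocol 9.1 (repeated in the Synopsis): a missing Month 12 height is "imputed from the last available height SDS, with a reduction of 2 cm/yr for subjects in the somavaratan group". The stated reason is that applying the reduction "only for the somavaratan imputed value avoids imputing to a common mean".

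SAP 6.4, primary analysis: "missing height at 12 months will be imputed from the last available height". There is no distinction by arm and no somavaratan reduction. The text continues: "This imputation assumes no growth after the last available measurement observed at study exit. This is an extremely conservative approach".

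SAP 6.4, sensitivity analysis: the reduction survives only as the fifth somavaratan option in the tipping-point grid: "Each subject imputed to HV based on last reported height, minus 2 cm (the non-inferiority margin, to avoid imputing to a common mean".

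SAP 4.1: "The primary analysis population (ITT, Intent-To-Treat) will be based on all randomized subjects". Protocol 9.3.3 limited the ITT population to children with at least one month of dosing and a completed Month 1 efficacy assessment.

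SAP Section 1 says the SAP supersedes the protocol and that differences will be described in Section 6.2. Section 6.2 lists four changes. The only one on missing data is: "Replaced multiple imputation for missing data with tipping point analysis". Neither the new primary imputation rule nor the new primary population appears.

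**The concern.** The null hypothesis in SAP 6.3 is that somavaratan minus daily rhGH is -2.0 cm/yr or less. Anything that lowers control height velocity raises this difference and helps to reject the null. Stopping growth at exit is harsh on somavaratan for a somavaratan drop-out but works in its favour for a control drop-out. Whether the rule is conservative therefore depends on which arm loses more children.

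The protocol's reduction kept imputed somavaratan values 2 cm/yr below what the same rule gives a control child. The SAP repeats the reason for this but removes it from the primary analysis.

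Higher control loss is foreseeable. The trial is open-label and compares daily injections with two a month, and Protocol Section 1 states: "A lack of compliance with daily rhGH administration is commonplace and can lead to loss of treatment effects". At stake is a claim of non-inferiority for a drug that is worse by the full margin, made at well above the nominal error rate.

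**Working it through.** **The SAP's own example.** A child leaves at Month 6 with an annualized velocity of 6 cm/yr: 6 × 6/12 = 3 cm over the year, or 3 cm/yr. This matches SAP 6.4.

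**Inputs.** Margin 2.0 cm/yr, SD 3.0 and one-tailed 0.025 (SAP 3.5). First-year velocity on daily rhGH 9.5–11 cm/yr (Protocol 1); 10 is used below. Arm sizes 63/21 (84 planned at 3:1) and 102/34 (Protocol 4.1). Drop-out by arm and time of exit are not in the documents and are assumed.

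**Shift from one drop-out under the SAP rule.** Shift in arm mean = velocity × (1 − t) / n, with t the fraction of the year completed.

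- Control, Month 6, n = 21: 10 × 0.5 / 21 = 0.24 cm/yr, 12% of the margin.
- Control, Month 3, n = 21: 10 × 0.75 / 21 = 0.36, 18%.
- Control with baseline height only, so velocity 0: 9.5/21 to 11/21 = 0.45 to 0.52 (23–26%); 9.5/34 to 11/34 = 0.28 to 0.32 (14–16%).
- Somavaratan, Month 6, n = 63, also at 10 cm/yr: 5/63 = 0.08, in the opposite direction.

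**How the two rules differ.** Take a Month 6 exit at 10 cm/yr and assume 5.5 cm/yr of growth afterwards when height SDS is held (an assumption; the documents give no figure).

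- Protocol rule: control 5 + 2.75 = 7.75; somavaratan 7.75 − 2 = 5.75.
- SAP rule: 5.0 in both arms.

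The SAP is no gentler on somavaratan drop-outs. The change acts mainly by pulling control drop-outs down from 7.75 to 5.0, and it removes the gap between the arms.

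**Expected difference when the truth is −2** (control 10, somavaratan 8, Month 6 exits):

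- 3/63 and 3/21 lost: −2 − 3×4/63 + 3×5/21 = −1.48.
- 5/102 and 7/34 lost: −2 − 5×4/102 + 7×5/34 = −1.17.
- 6/63 and 2/21 lost (9.5% each): −2 − 6×4/63 + 2×5/21 = −1.90.

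**False non-inferiority by simulation.** Same settings, 100,000 trials per case, pooled t-test without covariates, nominal 2.5%.

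| Lost: somavaratan, control | SAP rule | SAP freeze with 2 cm off somavaratan | Protocol 9.1 rule |
|---|---|---|---|
| 6/63, 2/21 | 2.2% | 0.8% | 1.4% |
| 0/63, 2/21 | 7.9% | 7.9% | 4.3% |
| 3/63, 3/21 | 7.9% | 5.2% | 3.4% |
| 5/102, 5/34 | 11.7% | 7.4% | 4.0% |
| 5/102, 7/34 | 23.9% | 16.9% | 6.1% |
| 8/63, 0/21 | 0.3% | 0.1% | 0.5% |

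Protocol-rule figures rest on the assumed 5.5 cm/yr. Within-arm imputation with 2 cm/yr taken off imputed somavaratan values gave 1.7–1.9% in a separate simulation of the 3/3, 5/5 and 5/7 cases.

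**The case against.** The documents do not predict unequal loss. The only planning figure is 8 drop-outs in 84, with no split by arm. The larger errors above need control loss at about three to four times the somavaratan rate. Milder patterns do less: 3/63 against 2/21 gives 4.5%, and Month 9 exits at 3/63 against 3/21 give 4.7%. The statement in Protocol Section 1 concerns compliance rather than withdrawal, and a non-compliant child who stays has a measured height. Controls also have a reason to stay, since completers may move to somavaratan in 13VR3, while injection-site pain (57.4% in Protocol Table 7) could raise loss on somavaratan.

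The simulation is also simplified. With the Welch test that SAP 6.11.1 allows, the 3/3, 5/5 and 5/7 cases fall to 6.7%, 10.1% and 20.6%. With SD 3.5 at 102/34, the last two become 10.1% and 19.5%. Exits before any post-baseline height should be rare: SAP 4.1 expects very few, and Protocol 4.4 and 7.3 ask early leavers to complete the Month 12 assessments.

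Finally, the tipping-point grid includes controls at their group mean against somavaratan frozen minus 2 cm. That cell gives about 1% error in the 3/3, 5/5 and 5/7 cases. The mITT and per-protocol analyses are run as well.

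This all bears on size, and the direction of loss is indeed unknown. It does not rescue the rule. Under none of these variations does error in the unequal-loss cases return to 2.5%, and two control losses with none on somavaratan already triple it. The grid is sensitivity only, and the SAP does not say what follows if its cells fail. The undeclared change stands whatever the drop-out pattern.

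**Conclusion.** The concern holds. The primary rule is not conservative for control drop-outs, and the SAP's description of it is wrong for a non-inferiority test. It removes the protocol's protection from the primary analysis without listing the change in SAP 6.2, and it is combined with an all-randomized population that can score an early control exit at 0 cm/yr.

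The size depends on the balance of loss. With about equal percentages lost, error stays near the nominal 2.5% (2.2%). With control loss at about three to four times the somavaratan rate and exits at Month 6, it is about 8% to 24%. If loss falls mainly on somavaratan, the rule is strict. These figures assume control 10 and somavaratan 8 cm/yr, SD 3.0 and no covariate adjustment. A primary analysis should not hold its error rate only when drop-out happens to be balanced.

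**What to change.** 1. In SAP 6.4, make the primary imputation multiple imputation within arm, using the model covariates and the interim heights, then subtract 2.0 cm/yr from every imputed somavaratan value and from no control value. This also gives a usable value for a child with baseline height only.
2. At minimum, restore the Protocol 9.1 rule (height SDS held, 2 cm/yr off for somavaratan only). This is weaker: error was still 3.4%, 4.0% and 6.1% in the 3/3, 5/5 and 5/7 cases. Adding the reduction to the freeze is not enough (5.2%, 7.4%, 16.9%).
3. Keep the no-growth rule as a sensitivity analysis and delete the statement that it is extremely conservative.
4. List both the imputation change and the population change in SAP 6.2, and state how the primary conclusion is read if tipping-point cells fail.

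Cost: SAP wording and standard imputation code before database lock, with no new data. If the drugs are truly equal, power falls from about 92% to 88% at 102/34 with 5% somavaratan loss. The cost at 63/21 was not worked out and should be checked, since power there starts lower, near 75%.

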6.11 EFFICACY ANALYSES

The primary efficacy analyses will be done using the All Randomized population, and will also be done using the mITT and PP populations.

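### In SAP 6.4, the sensitivity cell that fills both arms with their observed means has an SE too small by roughly the missing fraction, and no stated analysis with a valid variance covers that same assumption

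*SAP*

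**What the plan says.** The primary rule in SAP 6.4 assumes no growth after the last measurement: "For the primary endpoint in the ITT population, missing height at 12 months will be imputed from the last available height".

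The sensitivity analysis in the same section crosses three control-arm rules with five somavaratan rules, giving 15 comparisons.

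- Rule 1 in each arm uses the observed arm mean. For control: "All subjects to the control group mean (calculated without subjects missing endpoint".
- Rule 2 is a mixture: "50% to the group mean, 50% to the HV associated with each subjects last reported height (no additional gain in height".
- Rule 3 uses each subject's own last height.
- Somavaratan rules 4 and 5 subtract a further 1 or 2 cm, with a floor at zero height velocity.

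The SAP's example of a demanding combination is "control group imputation 1 versus somavaratan imputations 2 to 5".

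This grid took the place of another method. Protocol 9.1 had promised: "A sensitivity analysis using multiple imputation technique, assuming missing at random, will also be conducted". SAP 6.2, item 4, records the change: "Replaced multiple imputation for missing data with tipping point analysis". SAP 1 gives the SAP precedence over the protocol.

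On populations, SAP 6.11 says: "The primary efficacy analyses will be done using the All Randomized population, and will also be done using the mITT and PP populations". SAP 4.1 limits the mITT set: "Subjects completing less than one month of treatment or without a post-treatment height measurement will not be included in the mITT population". SAP 6.4 allows no imputation in the per-protocol set and gives no missing-data rule for mITT.

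**The concern.** Setting a missing value to its arm mean leaves the residual sum of squares unchanged, while the number of subjects and the degrees of freedom go up. The software then reports an SE as if every randomized child had been measured at Month 12. The SAP states no correction, so the interval for control 1 x somavaratan 1 is too narrow.

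The SAP does not label this cell missing at random. It is, however, the only one of the 15 that fills both arms from completers alone, so a reader will take it as the neutral reference beside a primary rule that the SAP itself calls extremely conservative. With the protocol's multiple imputation gone, nothing else in the plan clearly fills that role:

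- The primary analysis assumes no further growth.
- The per-protocol analysis also removes children who missed 10% or more of doses or had major deviations.
- The mITT analysis has no stated rule for a missing Month 12 height.

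**Working it through.** **Inputs.** SD 3.0 cm/yr, margin 2.0 cm/yr, 3:1 allocation, 57 + 19 = 76 evaluable and 84 planned (SAP 3.5, Protocol 9.2). At 3:1, 84 is 63 + 21, so the planned 8 dropouts are 63 − 57 = 6 and 21 − 19 = 2. Alpha is one-sided 0.05 in Protocol 9.2; SAP 3.5 adds a one-tailed 0.025. The documents state no SE for the mean-filled cell.

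**The plan's own figure.** Control n = (z_α + z_β)² × SD² × (1 + 1/3) / margin². The documents give no power; 80% is assumed here.

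- One-sided 0.05: (1.645 + 0.842)² × 9 × (4/3) / 4 = 18.6, rounded up to 19; 4 × 19 = 76, as stated.
- One-sided 0.025: (1.960 + 0.842)² × 3 = 23.6, rounded up to 24; total 96.

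The stated 76 therefore matches the protocol's alpha. The results below are given for both levels.

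**SE of the mean/mean cell, unadjusted.** Let n be the observed and N the randomized number.

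- SE the data support: 3 × √(1/57 + 1/19) = 0.795.
- SE reported: 3 × √[(76 − 2)/(84 − 2)] × √(1/63 + 1/21) = 0.718.
- Ratio: 0.718 / 0.795 = 0.904, so 9.6% too small, against a missing fraction of 8/84 = 9.5%.
- Half-widths at one-sided 0.025: 1.9925 × 0.7947 = 1.584 and 1.9893 × 0.7181 = 1.429. The lower limit is 0.155 cm/yr too favourable.
- One-sided error at the margin: P(T₇₄ > 1.9893 × 0.9036) = 3.8% for a nominal 2.5%. For a nominal 5%: P(T₇₄ > 1.6636 × 0.9036) = 6.9%.

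**Other amounts and splits of missing data** (same formulas; error is for a nominal 2.5%):

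| Randomized | Missing (somavaratan/control) | SE supported | SE reported | Too small by | One-sided error |
|---|---|---|---|---|---|
| 84 | 3/1 | 0.775 | 0.737 | 5% | 3.1% |
| 84 | 6/2 | 0.795 | 0.718 | 10% | 3.8% |
| 84 | 9/3 | 0.816 | 0.698 | 14% | 4.7% |
| 84 | 8/0 | 0.770 | 0.718 | 7% | 3.4% |
| 84 | 4/4 | 0.826 | 0.718 | 13% | 4.4% |
| 136 | 10/3 | 0.623 | 0.565 | 9% | 3.8% |

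**With ANCOVA.** In simulated trials with 6/2 missing and covariates assumed to explain 0, 20 or 40% of the variance, the model SE was 9 to 10% below the true value. The error was 3.6 to 3.9%. Complete-case ANCOVA on the same data held 2.4 to 2.6%.

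**The rest of the grid.** This simulation used assumptions outside the plan: 6/2 missing, control mean 10 cm/yr (Protocol 1 gives 9.5 to 11), true difference −2.0, linear growth, and non-informative dropout spread equally over Months 1, 3, 6 and 9. Reported SE divided by true SE:

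| | Som. 1 | Som. 2 | Som. 3 | Som. 4 | Som. 5 |
|---|---|---|---|---|---|
| Control 1 | 0.90 | 0.96 | 1.02 | 1.05 | 1.07 |
| Control 2 | 0.95 | 1.01 | 1.07 | 1.10 | 1.12 |
| Control 3 | 0.99 | 1.06 | 1.11 | 1.15 | 1.17 |

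Twelve of the 15 cells are about right or too large. The three below that are mean/mean and its two neighbours using the 50% rule. In control 1 x somavaratan 2 to 5, one-sided error was 1.4, 0.5, 0.3 and 0.2%.

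**The case against.** The strongest reply is that little turns on this. It is one sensitivity cell, and the combinations the SAP itself singles out have error below nominal under the assumptions above. With a true difference of 0, the mean/mean cell met the margin while the complete-case limit missed it in only about 6% of simulated trials at 84 subjects. The swap of methods is openly declared, and a completer-based per-protocol result without fills is still planned. All of this stands, and it is why the point is minor. It does not make the cell's interval correct, and the per-protocol set answers a narrower question.

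Stronger readings are tempting, but the documents do not support them:

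- *The whole grid is faulty.* It is not; see the second table.
- *Mean/mean is the mildest corner, where a tipping-point reading starts.* It is not. Control 3 x somavaratan 1 gives control dropouts no further growth and somavaratan dropouts the mean, which favours somavaratan more. With a true difference of 0 and otherwise the same assumptions, its average lower limit was −0.93 against −1.42 for mean/mean, and it was milder in over 99% of trials.
- *The SAP removed a missing-at-random analysis of all randomized subjects.* Protocol 9.3.3 limited its ITT set to children with at least one month of dosing and Month 1 assessments. The multiple imputation applied to that set. What was lost is the missing-at-random analysis on that set.
- *The non-inferiority decision is at risk.* The primary analysis uses the last-height rule, not the mean fill.

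**Conclusion.** The point holds and is minor. As written, the mean/mean cell will report an SE that is too small by roughly the missing fraction when dropout is proportional to arm size; more if dropout falls mainly in the control arm, less if mainly in somavaratan. The fault lies in its precision: unadjusted, the point estimate equals the complete-case estimate. The figures assume SD 3.0 and missingness unrelated to outcome within arm.

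The practical loss is that the plan states no analysis with a valid variance for the case where dropouts resemble completers in their arm. If the mITT analysis used only observed Month 12 heights, it would come close, but the SAP does not say so.

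**What to change.** Replace control 1 x somavaratan 1 with missing-at-random multiple imputation of all randomized subjects. Impute within arm from the primary-model covariates and whatever interim heights exist, and combine with Rubin's rules. Keep the adverse cells as stress scenarios.

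Optionally, add delta steps on the imputed somavaratan values, keeping the SAP's floor at zero height velocity. Report either the delta at which the lower limit crosses −2.0 cm/yr or that no crossing occurs before the floor. The second outcome is realistic. With a somavaratan mean of 10 and 6 of 63 imputed, the most the fills can move the difference is 10 × 6/63 = 0.95 cm/yr. Holding the half-width at 1.584, an observed difference above 0.95 − (2.0 − 1.584) = 0.54 in somavaratan's favour could not be tipped.

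The cost is SAP wording and a little more analysis with standard software; no new data are needed. The interval in this one result becomes slightly wider: half-width about 1.58 instead of 1.43 cm/yr unadjusted. Under ANCOVA with covariates assumed to explain 20% of the variance, it was about 1.42 to 1.49 instead of 1.32, the lower figures assuming interim growth that predicts Month 12 well. Simulated one-sided error with multiple imputation was 2.0 to 2.3% for a nominal 2.5%.
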